# 7.3.5 Pregnancy

- Details of all pregnancies in female participants after the start of study treatment and until at least 5 terminal half-lives after the last dose will be collected.
- If a pregnancy is reported, the Investigator should inform the Sponsor within 24 hours of learning of the pregnancy and should follow the procedures outlined in Appendix 4.
- Abnormal pregnancy outcomes (e.g., spontaneous abortion, fetal death, stillbirth, congenital anomalies, ectopic pregnancy) are considered to be SAEs.

#### 7.4 Treatment of Overdose

For this study, any dose of atomoxetine greater than 75 mg and of R-oxybutynin greater than 2.5 mg more frequently than QHS will be considered an overdose.

In the event of an overdose, the Investigator should refer to the approved product label for advice on overdose and:

- 1. Contact the Medical Monitor immediately.
- 2. Closely monitor the participant for AE/SAE and laboratory abnormalities until atomoxetine hydrochloride and/or R-oxybutynin chloride can no longer be detected systemically.
- 3. Obtain a plasma sample for PK analysis within 1 day from the date of the last dose of study treatment if requested by the Medical Monitor (determined on a case by case basis).
- 4. Document the quantity of the excess dose as well as the duration of the overdosing in the eCRF.

Decisions regarding dose interruptions or modifications will be made by the Investigator in consultation with the Medical Monitor based on the clinical evaluation of the participant.

#### 7.5 Pharmacokinetics

PK parameters are not evaluated in this study.

#### 8 Statistical Considerations

## **8.1** Sample Size Determination

A total of 58 patients will enter the 4-treatment crossover study. The study will have 80% power to detect a treatment difference at a two-sided 0.05 significance level, if the true difference between treatments on HB is at least -3.7 %min/h. This assumes that the within-subject standard deviation is 9, estimated from Study APN-006, and that the discontinuation rate is less than 20%.

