#### **Overall Design:**

Study APC-003 is a randomized, double blind, placebo-controlled, 4-period, single-dose crossover factorial study in patients with OSA. A screening visit and polysomnographic (PSG) exam will be conducted to establish that each participant meets study enrollment criteria. Each participant will then receive a single dose of each of the following during 4 overnight PSG exams, each separated by a one week washout period:

- Atomoxetine 75 mg + R-oxybutynin 2.5 mg (AD109)
- Atomoxetine 75 mg
- R-oxybutynin 2.5 mg
- Placebo

The primary hypothesis of the crossover study is that AD109 is superior to each of the other 3 arms, on the endpoint of Hypoxic Burden (HB), a measure of the depth and duration of the ventilatory disturbance in OSA.

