## 3 Endpoints

	Endpoints
Primary	Change in Hypoxic Burden (HB) 4%, (scored in reference to AHI 4%), AD109     vs. other 3 study treatments
Secondary	
 
Change in Apnea Hypopnea Index (AHI) 4%
 
Change in Oxygen Desaturation Index (ODI)
 
Total time with SaO2 <90%, PSG nights
 
Proportion of participants with ≥50% reduction, AHI, HB and ODI
 

Exploratory	
 
PSG sleep and arousal parameters
 
PSG respiratory parameters
 

Safety Endpoints	
 
Physical exam, vital signs, clinical laboratory assessment
 
Spontaneous adverse events, including the post-dosing period
 
DSST
 
PSG parameters: heart rate, ECG, EEG, oximetry
 

Abbreviations: AHI = apnea-hypopnea index; DSST = Digit Symbol Substitution Test; ECG = electrocardiogram; EEG = electroencephalogram; HB = Hypoxic Burden; ODI = Oxygen Desaturation Index; OSA = obstructive sleep apnea; PSG = polysomnography; SaO2 = oxygen saturation.

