4.5. Multiple Comparisons

Each group of endpoints for this study contains three hypothesis tests based on the study treatment: i) AD109 vs placebo, ii) AD109 vs R-oxybutynin, iii) AD109 vs atomoxetine. The type I error will be controlled by a fixed sequence procedure in which the hypothesis tests are conducted in the following order: i) AD109 vs placebo, ii) AD109 vs R-oxybutynin, iii) AD109 vs atomoxetine. Primary and secondary endpoints will be tested sequentially in the order they appear in Section 2.2.1 and Section 2.2.2. All hypothesis tests will test that the two-sided p-value is less than 0.05. All hypothesis tests for secondary endpoints will also be reported using the nominal 0.05 two-sided alpha level.

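### The stated 80% power is for one AD109 contrast at -3.7 %min/h; winning all three contrasts, as the protocol's primary hypothesis requires, has about 61% power if each true difference is -3.7

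*Protocol*

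**What the plan says.** Protocol 8.1 sets the size: "A total of 58 patients will enter the 4-treatment crossover study". It gives one power statement: "The study will have 80% power to detect a treatment difference at a two-sided 0.05 significance level". The effect size attached to that statement is worded "if the true difference between treatments on HB is at least -3.7 %min/h". On variability it says "This assumes that the within-subject standard deviation is 9, estimated from Study APN-006", and it adds that "the discontinuation rate is less than 20"%. SAP 9 repeats the paragraph, with the SD described as within-participant. Neither document names the contrast that the 80% refers to, gives a power for winning more than one contrast, or states a correlation between contrasts.

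The documents differ on what must be won:

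- **Protocol 1.1, Overall Design:** "The primary hypothesis of the crossover study is that AD109 is superior to each of the other 3 arms". The primary row of Protocol 3 likewise sets AD109 against all three other treatments on untransformed HB 4%. The rationale in 1.1 and 2.1 is to show that both components contribute, in support of a fixed-combination approval.
- **SAP 2.1.1 and 2.2.1:** the primary comparison is AD109 vs placebo only, on log10(HB[4%] + 1). The R-oxybutynin and atomoxetine contrasts are the first two secondary endpoints (SAP 2.2.2).
- **SAP 4.5:** "The type I error will be controlled by a fixed sequence procedure in which the hypothesis tests are conducted in the following order": placebo, then R-oxybutynin, then atomoxetine, each at two-sided 0.05.

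**The concern.** A power statement is useful when it refers to the hypothesis that the trial is meant to settle. Here the single figure is for one difference, while the protocol's primary hypothesis is a conjunction of three. Only AD109 vs atomoxetine shows that R-oxybutynin adds anything, and only AD109 vs R-oxybutynin shows that atomoxetine does. Under the SAP's sequence the atomoxetine contrast comes last, and it can be claimed only if the other two have been won. Each step uses the full 0.05, so the probability of completing the three HB steps equals the probability of winning all three.

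A sponsor, ethics committee or regulator who reads 80% as the chance of showing both contributions would overestimate it at the effect size that the plan uses. A missed atomoxetine contrast would also look more surprising than the plan's own inputs make it.

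**Working it through.** **Inputs from the documents (Protocol 8.1, SAP 9):** 58 entered; two-sided 0.05 (critical value 1.96); difference 3.7 in absolute value; SD 9; discontinuation at its 20% ceiling, so 58 × 0.8 = 46.4 completers.

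**Assumption not in the documents:** correlation 0.5 between contrasts. With equal, independent errors of variance σ² on each night, two contrasts that share the AD109 night have covariance σ² and variance 2σ² each, so the correlation is σ²/2σ² = 0.5. Other values are shown below.

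**Step 1. Reproduce the 80%.** Take 9 as the SD of the paired difference.

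- Non-centrality: 3.7 / (9/√46.4) = 2.80.
- Power: Φ(2.80 − 1.96) = 80.0%. At 46 completers it is 79.6%; a paired t-test with 46 gives 77.9%.
- Completers needed for 80%: (9 × 2.8016 / 3.7)² = 46.4, the same as 58 × 0.8.

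So the stated figure is the power of one pairwise contrast.

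**Step 2. Joint power with every true difference at -3.7.** This is the multivariate normal probability that all the z-statistics pass 1.96 in the right direction, when each contrast alone has 80%.

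| Correlation | Two component contrasts | All three contrasts |
|---|---|---|
| 0 | 64.0% | 51.2% |
| 0.3 | 66.6% | 57.0% |
| 0.5 | 68.7% | 61.1% |
| 0.7 | 71.3% | 65.9% |

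At 46 completers and correlation 0.5, all three have 60.6%. A paired-t simulation with 46 gives 57.4%. If none of the 58 drop out, a single contrast has 87.9% and all three have 74.3%.

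**Step 3. Differences that would give 80% jointly** (46.4 completers, correlation 0.5).

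| True differences vs placebo, R-oxybutynin, atomoxetine | Power for all three |
|---|---|
| 3.7, 3.7, 3.7 | 61% |
| 4.0, 4.0, 3.7 | 67% |
| 4.4, 4.4, 3.7 | 73% |
| 5.0, 5.0, 3.7 | 78% |
| 7.4, 7.4, 3.7 | 80% |
| 4.36, 4.36, 4.36 | 80% |

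**Step 4. The SD read as the text describes it.** If 9 is the SD of one night's value within a participant, the SD of a paired difference is 9 × √2 = 12.73. Non-centrality is then 3.7 / (12.73/√46.4) = 1.98. A single contrast has Φ(1.98 − 1.96) = 51%, and all three have about 26% at correlation 0.5.

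**The case against.** **The 80% is not wrong as written.** The sentence speaks of one treatment difference, and the figure reproduces. That stands. This is an omission and an unclear label, not an arithmetic error.

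**A reader might infer that the trial succeeds only if AD109 wins all three contrasts, so that its true power is 61%.** The documents do not support that as a general statement. It is the protocol's hypothesis, but the SAP's primary test is AD109 vs placebo alone, and for that test a single-contrast power is the right kind of figure. Under the SAP, all three wins are needed for the component-contribution claim, not for the primary result.

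**61% is one scenario.** It puts all three differences at exactly -3.7, which implies that neither component alone differs from placebo; the protocol says at least -3.7. It also assumes a correlation that the plan does not give, and dropout at its ceiling. The mITT set in SAP 4.2.2 keeps anyone with one primary measurement, so participants with incomplete data may add some information. All of this stands and is why a range is needed. It does not restore 80%: with both component differences at -3.7, even a very large placebo difference brings joint power only to about 69% at correlation 0.5, and full retention with all three at -3.7 gives 74%.

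**A reader might also infer that 80% holds jointly whenever only the atomoxetine difference is as small as -3.7.** It does not. Differences of 4.4, 4.4 and 3.7 give 73%. The other two must be far larger, for example about 7.4.

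**Nor does the finding show that the trial is too small.** Under the Step 2 assumptions, 80% for all three would need about 65 completers, or 82 entered (65/0.8 = 81.25, rounded up). Whether that target applies depends on which contrasts are primary and what differences are expected, and the documents do not settle either.

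**Conclusion.** The point holds in this form. The plan's 80% is the power of each single AD109 contrast at -3.7 %min/h, and no figure is given for the three-way claim in the protocol's primary hypothesis. With each true difference at -3.7, that power is about 61% (51% to 66% for correlations of 0 to 0.7; about 74% with no dropout). Put the other way, the chance of missing at least one contrast is about 39% at correlation 0.5.

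These figures rest on about 46 completers, a normal approximation, and 9 being the SD of the paired difference. The last assumption matters most: on the literal within-subject reading even the single-contrast figure falls to about 51%. All of the figures are for untransformed HB. They are not the power of the SAP's primary analysis on log10(HB[4%] + 1), for which the documents give no variance or effect size.

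**What to change.** No change in sample size, design or alpha. In Protocol 8.1 and SAP 9:

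1. State that the 80% applies to each single AD109 contrast on untransformed HB at -3.7 %min/h, with about 46 completers and 9 taken as the SD of the paired difference. Confirm this against Study APN-006. If 9 is the within-subject SD, replace the figures (about 51% single and 26% joint).
2. Add the joint power, with its assumptions. For example: if all three true differences are -3.7, power to win all three contrasts is about 61% with 46 completers and an assumed between-contrast correlation of 0.5 (51% to 66% for 0 to 0.7; about 74% if all 58 complete); 80% needs about -4.4 in all three, or placebo and R-oxybutynin differences far larger than 3.7, for example about 7.4.
3. Note that these figures are for untransformed HB and not for the log10(HB[4%] + 1) analysis.
4. Reconcile Protocol 1.1 and 3 with SAP 2.1 and 2.2 on which contrasts are primary.

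The first three items cost a few sentences in two places and a less favourable headline figure. The fourth needs a sponsor decision and matching text in both documents.

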## 1 Protocol Summary

## 1.1 Synopsis

**Protocol Title:** Phase 2 Randomized Double-Blind Placebo-Controlled 4-Period Single-Dose Crossover Factorial Study to Evaluate the Contribution of the Individual Drug Components to the Efficacy of the Combination of Atomoxetine and R-oxybutynin in Obstructive Sleep Apnea

**Sponsor Study No.:** APC-003

Phase: 2

**Sponsor:** Apnimed, Inc.

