4.4. Handling of Dropouts or Missing Data

Missing data will remain missing. No imputation of missing data will be performed.

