9. SAMPLE SIZE AND POWER CALCULATIONS

A total of 58 patients will enter the 4-treatment crossover study. The study will have 80% power to detect a treatment difference at a two-sided 0.05 significance level, if the true difference between treatments on HB is at least -3.7 %min/h. This assumes that the within-participant

¹ In the case that the total correct is 0, the participant will be dropped from the model.

standard deviation is 9, estimated from Study APN-006, and that the discontinuation rate is less than 20%.

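### The stated 80% power fits the planned pairwise tests only if 9 is the SD of the paired difference, but both documents label it the within-subject SD

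*Protocol*

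**What the plan says.** Protocol 8.1 and SAP 9 carry the same sizing paragraph: 58 participants enter the crossover. The SAP puts the claim as "The study will have 80% power to detect a treatment difference at a two-sided 0.05 significance level". The effect size is on untransformed hypoxic burden: "if the true difference between treatments on HB is at least -3.7 %min/h". The Protocol then gives the variability and the loss: "This assumes that the within-subject standard deviation is 9, estimated from Study APN-006, and that the discontinuation rate is less than 20" per cent. The SAP words the same sentence "This assumes that the within-participant" SD, again with the value 9. Neither document gives a formula, calls 9 the SD of a difference, or names the contrast that the power refers to.

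The tests are stated elsewhere. The Protocol synopsis (Overall Design) says "The primary hypothesis of the crossover study is that AD109 is superior to each of the other 3 arms". SAP 4.5 says "Each group of endpoints for this study contains three hypothesis tests based on the study treatment" and lists AD109 against placebo, R-oxybutynin and atomoxetine in fixed sequence, each at two-sided 0.05. SAP 6.1 estimates those three differences.

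**The concern.** In a crossover, the within-subject SD ordinarily means the residual SD of a single night's measurement once the participant's own level is removed. A comparison of two nights in the same participant carries two such residuals, so its SD is larger by √2. If 9 is entered in the sample-size formula as the SD of the difference but reported as the within-subject SD, the stated power does not follow from the stated inputs.

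This paragraph is the only justification for 58 participants. The trial exists to show that each component contributes, so the result against each single component matters. How to read a miss against one component depends on whether that contrast had about 80% or about 50% power. A later study sized from the label would also be about twice as large as one sized from an SD of differences of 9.

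**Working it through.** **Inputs.** N = 58, two-sided α = 0.05, power 80%, difference 3.7, SD 9, loss up to 20% (Protocol 8.1, SAP 9). The contrasts are pairwise (Protocol synopsis; SAP 4.5 and 6.1). The normal quantiles sum to 1.960 + 0.842 = 2.8016 before rounding.

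**Formulas.** With n complete pairs and SD_d the SD of the paired difference:
- completers needed = (2.8016 × SD_d / 3.7)²
- power ≈ Φ(3.7√n / SD_d − 1.960)
- difference detectable with 80% power = 2.8016 × SD_d / √n

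The ranges below run between the paired t and the normal calculation. Change from a common baseline does not matter, because the baseline cancels within a participant.

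**Step 1: reproduce the plan.** With SD_d = 9, (2.8016 × 9 / 3.7)² = 46.44 completers, and 46.44 / 0.8 = 58.05. This matches 58 and 80%. The implied residual SD is 9/√2 = 6.36.

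**Step 2: take the label as written.** With a residual SD of 9 and a common residual variance, SD_d = √2 × 9 = 12.73. Completers needed are (2.8016 × 12.73 / 3.7)² = 92.88, so 93, and 93 / 0.8 = 116.25, so 117 enrolled.

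**Step 3: compare the two readings at a difference of 3.7.**

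| Complete pairs | Power, SD_d = 9 | Power, SD_d = 12.73 | Detectable difference, SD_d = 12.73 |
|---|---|---|---|
| 46 | 77.9–79.6% | 48.8–50.5% | 5.26–5.37 |
| 47 | 78.8–80.5% | 49.7–51.3% | 5.20–5.31 |
| 58 (no loss) | 86.8–87.9% | 58.6–60.0% | 4.68–4.76 |

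With the larger residual degrees of freedom of a pooled crossover model, 3(n − 1) − 3, and SD_d = 12.73, power is 49.9%, 50.7% and 59.5% at 46, 47 and 58. These lie inside the same ranges.

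**Step 4: look for another reading that rescues a residual SD of 9.**
- A one-sided 0.05 test with 58 pairs gives 71.5%.
- AD109 against the mean of the other three arms has SD 9√(4/3) = 10.39 and gives 67.9% at 46.4 completers and 77.4% at 58.
- A factorial main effect (mean of two arms minus mean of the other two) has SD √(4 × 0.5²) × 9 = 9.0 and gives 80%. It is the only contrast tried that fits the label, and it is not a planned test.

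**The case against.** The strongest reply is the factorial one. The title describes a "4-Period Single-Dose Crossover Factorial Study to Evaluate the Contribution of the Individual Drug Components", and the power paragraph names no contrast. A main-effect contrast with a residual SD of 9 needs the same 46.44 completers, so the agreement with 58 cannot show how 9 was used: both figures could be right for a contrast that is not tested. That stands as a possible history. It does not rescue the paragraph, because the only stated hypotheses and tests are pairwise, and for those a residual SD of 9 gives 49–60%.

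The label may also be loose wording for the SD of differences, in which case one phrase needs changing. That is possible, and nothing here excludes it. The match to 58 is also close rather than exact: rounding completers up to 47 gives 59 enrolled, and a paired t-test needs 49 completers, or 62 enrolled. These gaps are small beside the √2.

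The number of pairs is uncertain in both directions. The mITT set keeps anyone with one primary measurement, so a participant who leaves after AD109 and one comparator still supplies that pair, and 20% discontinuation need not cost 20% of the pairs. Against that, SAP 4.4.1 drops HB on nights with less than 120 minutes of sleep, and SAP 4.4 says "No imputation of missing data will be performed". As an assumed illustration, a further 5% or 10% of completers without a usable pair leaves about 44 or 42 pairs (58 × 0.8 × 0.95 = 44.1; 58 × 0.8 × 0.90 = 41.8). Power is then 76–78% or 74–76% with SD_d = 9, and 47–49% or 45–47% with 12.73.

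**Conclusion.** The concern holds. For each planned AD109 contrast at 3.7 %min/h, the paragraph describes about 78–88% power if 9 is the SD of paired differences, and about 49–60% if 9 is the within-subject SD as labelled, over 46 to 58 complete pairs. As a statement about the planned tests, either the SD label or the power is wrong.

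The documents do not give the APN-006 variance estimate, so they cannot settle which, and this is not a finding that the trial is underpowered. The √2 step assumes a common residual variance. SAP 4.7 fits an unstructured covariance, under which each contrast can have its own SD of differences.

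A secondary point concerns scale. The stated power is for raw HB, which is the Protocol's primary endpoint. The SAP's primary test is on log10(HB + 1), with raw HB as a sensitivity analysis (SAP 2.2.1 and 6.1). No power is stated for that primary test, and none can be computed from the documents.

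**What to change.** Check in the APN-006 data which SD the 9 is, and make the same correction in Protocol 8.1 and SAP 9. In either case, say that the power refers to a pairwise AD109 contrast and state how many usable HB pairs it assumes.

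- If 9 is the SD of paired differences, label it so (implied residual SD about 6.4) and keep the 80%.
- If 9 is the residual within-subject SD, including the case where 80% was worked out for a main effect, restate pairwise power at 3.7 as about 50% with 20% loss and 60% with none. Alternatively, restate the detectable difference as about 5.2–5.4 %min/h with 20% loss and 4.7–4.8 with none.

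In SAP 9, also mark the raw-HB figure as belonging to the untransformed sensitivity analysis, and add power for the log10(HB + 1) primary contrast from the APN-006 SD of paired differences on that scale.

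The cost is one paragraph in each document and a short re-run on existing data. The sample size stays at 58 and no test changes, because the documents do not establish that 58 is too few. The stated power may become less favourable.

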# 8.2 Populations for Analyses

For the purposes of analysis, the following analysis sets are defined:

Population	Description
Enrolled	All participants who signed the ICF (including screening failures).
Modified Intent to Treat (mITT) Population	The mITT Population comprises all participants who are randomized, take at least 1 dose of any of the study treatments, and have at least 1 measurement on the primary endpoint.  Participants will be analyzed for efficacy according to the randomly assigned treatment for each period.
Safety Population	The Safety Population consists of all participants who are randomized and receive at least 1 dose of any of the study treatments. Participants will be analyzed for safety based on the treatment received for each period. A precise definition of "as actually received" will be added in the Statistical Analysis Plan (SAP).
Per Protocol (PP) Population	The PP Population consists of all participants without any major protocol violations that could influence efficacy assessment. Participants in this population will be analyzed according to the treatment they actually received for each period. Treatment received is defined as the actual treatment taken during each period

# 8.3 Interim Analyses

No interim analysis is planned.

# 9 Supporting Documentation and Operational Considerations

## 9.1 Appendix 1: Regulatory, Ethical, and Study Oversight Considerations

# 9.1.1 Regulatory and Ethical Considerations

- This study will be conducted in accordance with the protocol and with:
  - Consensus ethical principles derived from international guidelines including the Declaration of Helsinki and Council for International Organizations of Medical Sciences International Ethical Guidelines.
  - Applicable International Conference on Harmonisation (ICH) Good Clinical Practice (GCP) Guidelines.

- Applicable laws and regulations.
- The protocol, protocol amendments, ICF, Investigator's Brochure, and other relevant documents (e.g., advertisements) must be submitted to an IRB/IEC by the Investigator and reviewed and approved by the IRB/IEC before the study is initiated.
- Any amendments to the protocol will require IEC/IRB approval before implementation of changes made to the study design, except for changes necessary to eliminate an immediate hazard to study participants.
- The Investigator will be responsible for the following:
  - Providing written summaries of the status of the study to the IRB/IEC annually or more frequently in accordance with the requirements, policies, and procedures established by the IRB/IEC.
  - Notifying the IRB/IEC of SAE or other significant safety findings as required by IRB/IEC procedures.
  - Overall conduct of the study at the site and adherence to requirements of 21 Code of Federal Regulations (CFR), ICH GCP guidelines, the IRB/IEC guidelines, European regulation 536/2014 for clinical studies (if applicable), and all other applicable local regulations.

